### 8.2. Exclusion Criteria

A subject will not be eligible for inclusion in this study if any of the following criteria are met:

- (1) Subjects with excessive daytime sleepiness due to conditions other than Parkinson's disease (including narcolepsy)
- (2) Subjects with significant eye disease which may substantially impact the subject's mobility and ability to have eye examination conducted as per investigator's judgement.
- (3) Subjects with a recent history of suicide attempt (defined as an active, interrupted or aborted attempt within the past 1 year), or reports suicidal ideation in the past 3 months as indicated by a positive response on the C-SSRS at screening visit (an answer of 'yes' to any of the 6 questions)
- (4) Subjects with clinical evidence of depression with significant psychiatric comorbidities (Hamilton Rating Scale for Depression − HAM-D score ≥ 17; with or without treatment)
- (5) Subjects with evidence of significant Cognitive Impairment (Montreal Cognitive Assessment MoCA score ≤ 22 at screening)
- (6) Subjects with evidence of significant fatigue (Fatigue Severity Scale  $FSS \ge 36$ )
- (7) Subjects with high risk of sleep apnoea (Berlin questionnaire with  $\geq 2$  categories where the score is positive)
- (8) Subjects taking any of the following prohibited medications at screening:
  - Alerting agents, including r-modafinil, modafinil or methylphenidate
  - Benzodiazepines
  - Histamine active agents
  - Hypnotics
  - Cholinergics
  - Skeletal muscle relaxants
  - Clozapine
  - Atomoxetine
  - Amitriptyline
  - Any other daytime medications which affect sleep
- (9) Subjects with chronic oral and / or ophthalmic steroidal use
- (10) Subjects with either renal or hepatic impairment defined by laboratory parameters >1.5x age-adjusted limits of normal range

Protocol No.: BB-2001-201b EudraCT No.: 2017-000877-35 Amendment 04, Final Version 1.0 07/Nov/2018 Page 45 / 142

- Hepatic damage: Alanine aminotransferase [ALT], aspartate aminotransferase [AST], alkaline phosphatase, or total bilirubin
- Renal damage: Blood creatinine, blood urea nitrogen [BUN], or estimated glomerular filtration rate [eGFR] < 60 mL/min/1.73m2
- (11) Subjects with abnormal ECG time intervals at baseline including QTc (> 450 for males and > 470 for females)
- (12) Subjects with known history of lung malignancy.
- (13) Subjects with known history of abuse of alcohol or other addictive substances in the 6 months prior to inclusion.

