# **8.4.1.7 Vital signs**

Vital signs (respiratory rate, height, weight and BMI) will be assessed at all study visits (screening, visit 2 (day 14), visit 3 (day 42) or early termination, and follow-up. Blood pressure (both systolic and diastolic and heart rate) will be assessed at the same visits but this is considered for this protocol as specific cardiovascular assessment (see later).

Amendment 04, Final Version 1.0
Protocol No.: BB-2001-201b
EudraCT No.: 2017-000877-35
Page 48 / 142

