### 8.4.1.12 Electrocardiogram, heart rate, blood pressure

A 12-lead ECG will be performed locally at screening and visit 3 (day 42) or early termination. Additional ECGs may be performed at the discretion of the investigator during follow-up. The findings and any abnormality will be recorded in the eCRF as either medical history (findings at screening) or adverse events (any further finding or change from screening). Standard ECG parameters will be recorded in the eCRF (heart rate, RR, QT, QTc following both Bazzett's and Fridericia's methods).

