12 STATISTICAL METHODOLOGY FOR SAFETY ENDPOINTS

The baseline value is defined as the last available value before the first dose of double-blind IMP taken.

The analysis of the safety variables will be essentially descriptive and no systematic testing is planned.

The observation period of safety data will be divided into 2 sub-periods:

- The pre-treatment period is defined as the time between the date of signed informed consent and the first dose of double-blind IMP.
- The on-Treatment period (TEAE period): is defined as the Date/ time from first dose of double-blind IMP.

12.1 Incidence of Adverse Events (AEs), Serious Adverse Events (SAEs), and Adverse Events of Special Interest (AESIs) such as headache, nausea and insomnia

All adverse events will be analysed and determined to be either pre-treatment or treatment-emergent. If an adverse event date/time of onset (occurrence, worsening, or becoming serious) is incomplete, an imputation algorithm will be used to classify the adverse event as pre-treatment or treatment-

emergent. The algorithm for imputing date/time of onset will be conservative and will classify an adverse event as treatment emergent unless there is definitive information to determine it is pre-treatment.

All adverse events (including serious adverse events and adverse events of special interest) will be coded to a lower-level term (LLT), preferred term (PT), high-level term (HLT), high-level group term (HLGT), and associated primary system organ class (SOC) using the version of Medical Dictionary for Regulatory Activities (MedDRA) version 20.1. Lower-level term (LLT) will not be presented in the analysis. Number of patients in the SAF will be used as denominator for the percentages calculation.

12.2 Incidence of suicidal ideation (C-SSRS) findings from screening/baseline to the end of the 2-week and the 6-week treatment period and safety follow-up

Patients with a positive response on the C-SSRS (an answer of ‘yes’ to any of the 6 questions) will be described through absolute frequency and percentage at visit 2 (day 14) , visit 3 (day 42) and globally (at any time in the follow-up period) in the study. This percentage will be calculated using the number of patients with C-SSRS evaluation done at the corresponding visit as denominator.

12.3 Incidence of positive psychotic symptoms (BPRS+) findings from screening/baseline to the end of the 2-week and the 6-week treatment period and safety follow-up

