12.6 Incidence of cardiovascular safety findings (blood pressure, heart rate, ECG QT/QTc)

Incidence of Potentially Clinically Significant Abnormality (PCSA) as detailed below will be described for blood pressure and ECG:

- Blood Pressure
 - SBP: ≤ 95 mmHg or decrease from baseline ≥ 20 mmHg or ≥ 160 mmHg or increase from baseline ≥ 20 mmHg
 - DBP: ≤ 45 mmHg or decrease from baseline ≥ 10 mmHg or ≥ 110 mmHg or increase from baseline ≥ 10 mmHg
- Heart rate
 - < 50 bpm or decrease from baseline ≥ 20 bpm or ≥ 100 or increase ≥ 20 bpm from baseline.
- ECG
 - QTc (> 450 for males and > 470 for females) for both Bazett and Friedericia.
 - QT > 500

Incidences will be calculated using the number of patients in the safety population as denominator.

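### SAP 12.6 pools high and low findings in one category each for blood pressure and heart rate, and its 500 limit on uncorrected QT leaves QTc above 500 without a row of its own

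*SAP*

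**What the plan says.** SAP 12.6 lists the potentially clinically significant abnormalities (PCSAs) whose incidence is to be described.

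- Systolic pressure: "SBP: ≤ 95 mmHg or decrease from baseline ≥ 20 mmHg or ≥ 160 mmHg or increase from baseline ≥ 20 mmHg".
- Diastolic pressure: "DBP: ≤ 45 mmHg or decrease from baseline ≥ 10 mmHg or ≥ 110 mmHg or increase from baseline ≥ 10 mmHg".
- Heart rate has the same four-part form: below 50 bpm, a fall of 20 or more, 100 or above, or a rise of 20 or more.
- ECG: "QTc (> 450 for males and > 470 for females) for both Bazett and Friedericia", and separately a limit of 500 on QT, with no correction and no unit stated.

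The denominator is the safety population. No visit rule is given. For safety data, SAP 12 states: "The baseline value is defined as the last available value before the first dose of double-blind IMP taken".

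On data collection, Protocol 8.4.1.12 states "A 12-lead ECG will be performed locally at screening and visit 3 (day 42) or early termination" and "Standard ECG parameters will be recorded in the eCRF (heart rate, RR, QT, QTc following both Bazzett's and Fridericia's methods". Protocol 8.4.1.7 puts vital signs at screening, Visit 2, Visit 3 or early termination, and follow-up, and adds: "Blood pressure (both systolic and diastolic and heart rate) will be assessed at the same visits". At entry, exclusion 11 removes "Subjects with abnormal ECG time intervals at baseline including QTc (> 450 for males and > 470 for females"; it does not name a correction.

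**The concern.** Blood pressure, heart rate and QT/QTc are named safety endpoints (Protocol 6.2.2, SAP 11). Protocol 7.2 justifies measuring pressure and heart rate at every visit by the orthostatic and other cardiovascular changes common in Parkinson's disease, so direction matters here. One incidence that mixes falls with rises cannot show which of the two a dose produces. It also carries the background of both directions, and a drug effect in one direction reduces the flags in the other.

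The absolute limits have no baseline condition, and Protocol 8.1 and 8.2 contain no blood pressure entry criterion. A subject with a systolic pressure of 160 or more before dosing, and unchanged after it, is therefore counted as a finding.

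On the ECG, uncorrected QT shortens as heart rate rises. A 500 limit on it picks out different subjects from a 500 limit on QTc, although both corrected values are collected.

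**Working it through.** **1. Neighbouring sections.** SAP 12.4 counts respiratory rate only when normal at baseline and abnormal at Visit 3, and physical findings only as normal to abnormal. SAP 12.5 uses shift tables of below, within and above normal. SAP 12.6 has neither a baseline condition nor a split by direction.

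**2. Background rate with no drug effect.** The plan states no expected rate, so there is no figure to reproduce. From the documents: the rules above, one baseline value, and up to three post-baseline readings (Visit 2, Visit 3, follow-up). Assumed, because the documents give nothing: within-subject visit SD *w* of 7-12 mmHg (systolic) and 5-8 (diastolic); mean (between-subject SD) 130 (13) and 78 (8); values rounded to 1 mmHg.

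At one visit, the change criterion alone gives P = 2[1 − Φ((d − 0.5)/s)] with s = √2·w.

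- Systolic, d = 20: w = 7 gives s = 9.9 and P ≈ 5%; w = 12 gives s = 17.0 and P ≈ 25%.
- Diastolic, d = 10: w = 5 gives s = 7.1 and P ≈ 18%; w = 8 gives s = 11.3 and P ≈ 40%.

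The full rule, including absolute limits, simulated with 400,000 subjects:

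| | one visit | any of 2 | any of 3 |
|---|---|---|---|
| Systolic | 8-29% | 13-46% | 18-57% |
| Diastolic | 18-40% | 30-61% | 39-74% |

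For the change criterion alone to reach 50% at one visit (ignoring rounding), s would have to be 20/0.6745 = 29.7 mmHg (systolic) or 10/0.6745 = 14.8 mmHg (diastolic).

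**3. Dilution.** Take an assumed systolic rise of 8 mmHg, s = 14, one visit, change criterion only.

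- Rises of 20 or more: 1 − Φ(20/14) = 7.7% without the effect; 1 − Φ(12/14) = 19.6% with it. Difference 11.9 points, ratio 2.6.
- Falls of 20 or more: 7.7% becomes Φ(−28/14) = 2.3%.
- Pooled: 15.3% becomes 21.8%. Difference 6.5 points, ratio 1.4.

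For diastolic pressure, assume a 5 mmHg rise at Visits 2 and 3, w = 6, mean 76, between-subject SD 8, counted over three visits. The pooled rate moves from 54% to 62%. High/rise alone moves from 28% to 47%, while low/fall drops from 28% to 18%.

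**4. QT against QTc.** QTcF = QT/RR^(1/3), QTcB = QT/RR^(1/2), RR = 60/heart rate.

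- 80 bpm, RR = 0.75: QTcF 500 is a QT of 500 × 0.75^(1/3) = 454. QT reaches 500 only at QTcF 500/0.75^(1/3) = 550.
- 75 bpm, RR = 0.80: QTcF 500 is QT 464, and QTcB 500 is QT 447. A QT of 470 gives QTcF 506 and does not meet the 500 line.
- 50 bpm, RR = 1.20: QT 500 is QTcF 471 and QTcB 456, so the line is met with QTc well below 500.

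Above 60 bpm, QTc passes 500 before QT does; below 60 bpm the order reverses. Any QTc above 500 also exceeds 450 and 470, so that subject is still counted in the QTc row.

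**5. Entry against analysis.** At 70 bpm (RR = 0.857), QTcF 440 is QT 418 and QTcB 451.5. If a site judged a man eligible on Fridericia, he would meet the Bazett row with no change from screening. Exclusion 11 neither permits nor prevents this.

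**6. After splitting** (assumptions as in step 2, no drug effect). At one visit: systolic high 4-15% and low 3-14%; diastolic high and low 9-20% each. At any of three visits: systolic 10-32% and 8-29%; diastolic 20-39% each.

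**The case against.** Safety analysis is descriptive and shown by arm beside placebo, so readers can see the background rate. Protocol 11.1.7 asks for vital-sign and cardiovascular changes to be described and judged for clinical significance, and SAP 7 sets numerical summaries that include the mean. Protocol 8.4.1.12 records ECG changes from screening as adverse events. The table shells are a separate document (SAP 17) and may already split the criteria. All of this stands, and it limits the harm: direction is lost in the PCSA incidence, not necessarily everywhere in the report. It does not remove the point. SAP 1 says the plan should be precise enough to guide programming, and 12.6 as written calls for one pooled category per parameter.

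A reader might infer that about half of all subjects would be flagged by chance. The documents do not support that. They give no blood pressure variability and no any-visit rule, and 12.4, next to it, looks at Visit 3 only. The three-visit count also includes follow-up, 28 days after the last dose.

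A reader might also infer that subjects with QTc above 500 are missed. They are not; they fall in the 450/470 row. What is lost is the severity tier.

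Finally, exclusion 11 uses the same 450/470 limits, so many baseline exceedances are removed at entry. The Fridericia-admitted, Bazett-flagged case needs a site to have screened on one correction only, which no section states.

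**Conclusion.** The point holds for the PCSA incidences in SAP 12.6. As written, they cannot separate low from high findings in blood pressure or heart rate, they count pre-existing exceedances of the absolute limits, and they shrink a one-directional effect: in the worked systolic case from a ratio of 2.6 to 1.4, in the diastolic case from a 19-point to an 8-point contrast. The pooling, the missing baseline condition and the missing visit rule are visible in the text and need no assumption. The sizes rest on the assumed SDs and effects.

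The background rate may be high, but the supportable statement is a range: 8-29% (systolic) and 18-40% (diastolic) at one visit, 18-57% and 39-74% over three. No single figure should be quoted as the plan's chance rate. The QT limit leaves QTc above 500 uncounted as a tier of its own; it does not drop those subjects. No efficacy or tested conclusion depends on this. It is worth correcting because these categories are how a named safety endpoint will be read.

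**What to change.** In SAP 12.6 and the table shells:

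- Tabulate low/fall and high/rise as separate categories for systolic pressure, diastolic pressure and heart rate, keeping the plan's own limits.
- Show each by visit and at any on-treatment visit, and say how the follow-up reading is handled.
- Count absolute limits only in subjects not beyond them at baseline, and state the denominator. Apply the same condition to QTc 450/470, using the same correction at baseline and after.
- Add QTc > 500 rows for Bazett and for Fridericia, beside or in place of the uncorrected QT row, and state the unit.

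All values are already collected, so the cost is SAP and shell wording and a few more table rows.

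Separately, exclusion 11 names no correction while SAP 12.6 applies two. The sponsor should reconcile these passages. Any change to exclusion 11 is a protocol eligibility change, not SAP wording, and would go through the amendment procedure in Protocol 10.2.

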11 SAFETY ENDPOINTS

The safety analysis will be based on the reported adverse events and other safety information, such as clinical laboratory data and physical examination as described in the protocol.

The safety of Bavisant compared to placebo will be assessed by the evaluation of the following:

- Incidence of Adverse Events (AEs), Serious Adverse Events (SAEs), Serious and related Adverse Events and Adverse Events of Special Interest (AESIs) headache, nausea and insomnia
- Incidence of suicidal ideation (C-SSRS) findings from screening/baseline to the end of the 2-week and the 6-week treatment period and safety follow-up
- Incidence of positive psychotic symptoms (BPRS+) findings from screening/baseline to the end of the 2-week and the 6-week treatment period and safety follow-up
- Incidence of physical examination, vital signs and laboratory tests changes from normal to abnormal (haematology and biochemistry)
- Incidence of cardiovascular safety findings (blood pressure, heart rate, ECG including QT/QTc)

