12.4 Incidence of physical examination, vital signs

Physical examinations will consist of the following body systems: (1) general, appearance; (2) extremities; (3) skin; (4) head and neck; (5) eyes, ears, nose and throat; (6) lungs and chest; (7) heart/ cardiovascular; (8) neurological; (9) abdomen / gastrointestinal; (10) liver; (11) musculoskeletal; and (12) other. Each system should be assessed as normal or abnormal and in the last case if that is clinically relevant or not. The incidence of patients with at least one change from normal at baseline to abnormal at Visit 3 will be calculated for each of the body systems.

Potentially Clinically Significant Abnormality (PCSA) are detailed below for Vital signs:

- WEIGHT change from baseline >5%
- Number of breaths per minute <12 or >25. Percentages of patients with a normal respiratory rate (RR) at baseline and an abnormally high or low RR at Visit 3 will be summarized by treatment.

Incidences will be calculated using the number of patients in the safety population as denominator.

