12.5 Incidence of laboratory tests findings (haematology and biochemistry)

Clinical laboratory values after conversion will be analysed into standard international units and international units will be used in all listings and tables. Shift tables will be produced presenting the intra-patient change between below normal, normal and above normal for each of the laboratory parameters, according to the appropriate laboratory ranges.

Incidences will be calculated using the number of patients in the safety population as denominator.

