12.7 Incidence of eye exam findings

Incidence of patients with any new finding on ophthalmological examination in the follow up period will be calculated. Detailed listings of all baseline and on-treatment ophthalmological findings will be provided

Incidences will be calculated using the number of patients in the safety population as denominator.

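### SAP 12.6 reports QTc only as an absolute exceedance: no change from baseline is shown, and the row for a formula not used at entry may include elevations already present at screening

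*SAP*

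**What the plan says.** The QTc criterion in SAP 12.6 is "QTc (> 450 for males and > 470 for females) for both Bazett and Friedericia". The only other ECG criterion is an absolute, uncorrected QT above 500. For both, "Incidences will be calculated using the number of patients in the safety population as denominator". SAP 12 does define a safety baseline ("The baseline value is defined as the last available value before the first dose of double-blind IMP taken"), but the QTc item does not use it. Safety is otherwise descriptive: "The analysis of the safety variables will be essentially descriptive and no systematic testing is planned".

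Other safety items look at change:
- SAP 12.6 adds change-from-baseline limits for systolic pressure (20 mmHg), diastolic pressure (10 mmHg) and heart rate (20 bpm) to the absolute ones.
- SAP 12.4 reports "Percentages of patients with a normal respiratory rate (RR) at baseline and an abnormally high or low RR at Visit 3".
- SAP 12.5: "Shift tables will be produced presenting the intra-patient change between below normal, normal and above normal for each of the laboratory parameters".
- SAP 12.7: "Incidence of patients with any new finding on ophthalmological examination in the follow up period will be calculated".

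Protocol 11.1.7 says that cardiovascular changes will be described by treatment group, and protocol 8.4.7 places QT/QTc among the cardiovascular findings. SAP section 14 declares no departure from the protocol's statistical content.

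Protocol 8.4.1.12 schedules an ECG at screening and at Visit 3 or early termination, with both Bazett and Fridericia values entered in the eCRF. Exclusion 11 (protocol 8.2) bars subjects above 450 (men) or 470 (women) and does not say by which formula.

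**The concern.** QTc is the one cardiovascular item in SAP 12.6, apart from the raw QT limit, that is judged without reference to the subject's own starting value. Two kinds of information are lost.

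First, someone reading the row for a formula that a site did not use for eligibility cannot separate elevations that arose on treatment from those already there at screening.

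Second, the size of any QTc shift is invisible. A large rise that ends below the limit is not counted, and a further rise in someone already above it leaves the count unchanged. In a three-dose study, QTc change by dose is what a safety reader would want, and protocol 11.1.7 leads that reader to expect it.

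**Working it through.** The documents give no figure for the QTc table, so there is nothing to reproduce. The check is whether a subject can be within the entry limit by one formula and above the table's limit by the other, and what the table leaves out.

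**Inputs.** The limits 450/470 come from SAP 12.6 and exclusion 11. Planned size is 230 randomised 1:1:1:1, with about 15% early withdrawal (protocol 8.0). Heart rates and QT values below are assumptions; the documents give none.

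**Formulas.** RR = 60/HR in seconds; QTcB = QT/RR^(1/2); QTcF = QT/RR^(1/3). The QT at which each formula reaches a limit L is L × RR^(1/2) for Bazett and L × RR^(1/3) for Fridericia.

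| Sex (limit) | HR per min | QT where QTcB reaches limit (ms) | QT where QTcF reaches limit (ms) | Whole-ms QT where the formulas disagree |
|---|---|---|---|---|
| Man (450) | 50 | 493.0 (492.95 unrounded) | 478.2 | 479 to 492, high by Fridericia only |
| Man (450) | 60 | 450.0 | 450.0 | none |
| Man (450) | 70 | 416.6 | 427.5 | 417 to 427, high by Bazett only |
| Man (450) | 80 | 389.7 | 408.9 | 390 to 408, high by Bazett only |
| Man (450) | 90 | 367.4 | 393.1 | 368 to 393, high by Bazett only |
| Woman (470) | 80 | 407.0 | 427.0 | 408 to 427, high by Bazett only |

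**Carry-over.** A man at 80/min (RR 0.75) with QT 400 has QTcB 461.9 and QTcF 440.3. If his site judges exclusion 11 by Fridericia he is randomised. If nothing changes, he is counted in the Bazett row at Visit 3. If the site requires both values to be within limits, he is excluded, and only eligibility breaches could carry over.

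**Worsening above the limit.** A man at 80/min moving from QT 415 to 445 goes from 479.2 to 513.8 by Bazett (+34.6) and from 456.8 to 489.8 by Fridericia (+33.0). Being above 450 by both formulas at the start, he could be in the study only through an entry breach. He would be counted either way, and nothing shows the rise.

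**Rise below the limit.** At 60/min RR = 1, so both corrected values equal QT. A man moving from 400 to 440 gains 40 ms and is never counted.

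**Weight of one case.** 230/4 = 57.5 per arm, and 1/57 = 1.75%. If all the expected withdrawals lacked a post-dose ECG, 57.5 × 0.85 = 48.9 would be evaluable, and 1/49 = 2.04%. So one subject is about 1.8% to 2.0%, depending on the denominator.

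**The case against.** The strongest reply rests on exclusion 11. It uses the table's own cut-offs and is reconfirmed before randomisation, so in a correctly enrolled subject an exceedance on the eligibility formula is new by design. This stands. A reader might infer from the missing baseline condition that the table can never tell a new elevation from an old one; the documents do not support that. The doubt is confined to a formula not used at entry and to eligibility breaches. It can also be argued that, with both values recorded on every ECG, the natural reading of exclusion 11 is that either abnormal value excludes. That is possible, but the protocol does not say so.

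The other replies go less far:
- **Protocol commitment.** Protocol 11.1.7 already promises cardiovascular changes by arm. That supports adding the display, because SAP 12.6, followed as written, produces none for QTc.
- **Baseline summaries.** SAP 13.1 has baseline safety parameters presented with the summary statistics. A group summary does not link a counted subject to his or her own starting value.
- **Medical history and adverse events.** Protocol 8.4.1.12 sends screening ECG findings to medical history and later ones to adverse events. Protocol 9.1.2 limits ECG adverse events to changes judged clinically significant, although that includes anything the investigator considers beyond normal fluctuation. Some individual changes will surface this way, but not QTc change by arm and formula.
- **Table shells.** These are separate documents (SAP 17) and may include a baseline column. They cannot be checked here, and the SAP text does not require one.

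**Conclusion.** The point holds as a minor gap in reporting. SAP 12.6 shows no QTc change, although the protocol says cardiovascular changes will be described and the section gives its other cardiovascular measures change limits. For a formula not used at entry, the count may also mix old and new elevations.

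The size of that mixing cannot be derived. It depends on how sites apply exclusion 11 and on the heart rates and QT values enrolled, and it may be near zero. The disagreement bands show that it is possible at ordinary heart rates, not that it is common.

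A reader might also infer a bias between arms. That does not follow: allocation is randomised, so pre-existing elevations are not systematically placed in one arm, and no safety testing is planned. The primary ESS analysis is unaffected.

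**What to change.** Keep the absolute count in SAP 12.6 and add, separately for Bazett and Fridericia and by arm:

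1. A descriptive summary of QTc change from the last pre-dose (screening) ECG to the post-dose ECG at Visit 3 or early termination. This captures rises below the limit and worsening above it.
2. A baseline-to-post-dose shift table at 450 (men) and 470 (women). Equivalently for new elevations, count those above the limit after dosing among subjects at or below it at baseline by the same formula who have a post-dose ECG, with those subjects as the denominator.

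The cost is a few lines of SAP text and slightly more tabulation. Both QTc values are already in the eCRF, so no extra ECG, new data item, eligibility change or protocol amendment is needed.
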